9.2 Anticipated and Unanticipated Adverse Device Effects

PrismRA arm:

PrismRA is not expected to result in either anticipated or unanticipated adverse device effects (UADE) as it involves the analysis of ex-vivo blood samples from the participating patients.

This study does include a potential source of harm to the patient as a result of the venipuncture procedure, unrelated to the study device:

- Faintness, inflammation of the vein, bruising, temporary discomfort, and bleeding at the site of puncture may occur.
- Infection may also occur, though rare.

External control arm:

Data arise from routine clinical practice and do not involve the use of the PrismRA test. Thus, no study-relevant adverse device effect exists.

10 Statistical Considerations

Data collected throughout this study will be analyzed by Sponsor or its designee.

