5.2 Analysis Populations

PrismRA arm:

This arm will enroll approximately 600 RA patients at approximately 33 clinical sites who are at least 18 years of age. All patients in the PrismRA arm will undergo PrismRA testing at their first study visit (Visit 1). See Section 6.1.1 and 6.1.2 for patient inclusion and exclusion criteria for details.

This study will perform analyses for two sets of populations from the PrismRA arm. The first one is the modified ITT analysis population, which consists of patients that initiate the study

treatment at Visit 2. A sub-population of patients who are adherent to the PrismRA test results will also be analyzed. This sub-population will exclude patients who initiated TNFis despite having a PrismRA result indicating a molecular signature of non-response to TNFi therapies.

External control arm:

Patients with RA in the OM1 PremiOM RA Dataset will be selected based on the same eligibility criteria as in the PrismRA arm and adapted for real-world data availability where necessary. Patients in the external control arm will be balanced with patients in the PrismRA arm using a propensity score (PS) model developed with the primary goal of achieving balance in baseline characteristics between the comparison groups. The external control arm is expected to have at least 1,500 eligible patients, with no less than 750 patients having CDAI scores at both baseline and Week 24. Data from patients who initiated b/tsDMARDs in the contemporaneous period (March 2022 and onward) will be used and if needed, the recent historical period (6-month to 3-year period prior to March 2022) will be used to maximize the size of the patient pool while minimizing confounding by the potential secular trends in treatment patterns. The PS model building process will aim to retain the inclusion of as many PrismRA arm participants as possible. If less than 95% of the PrismRA arm is included due to the lack of a matched control or non-overlapping PS, the historical period will be used for identifying external control patients. The smallest historical time window that can retain inclusion of greater than 95% of PS matched PrismRA patients will be used. The overlap in PS distributions between the external control and PrismRA arms will inform the ultimate sample size.

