5.5 Statistical Bias Reduction

Studies using observational data are prone to multiple biases. These potential biases in this study are addressed as described below.

Selection Bias. To minimize selection bias for identifying an external control arm for a clinical trial, the study was designed using the target trial emulation framework. [14] The external control arm inclusion/exclusion criteria are carefully defined and matched to the PrismRA arm to reduce potential selection bias. All available patients in the external control arm meeting the criteria for selection will be used in the analyses.

The design of the study is aimed to emulate a randomized clinical trial as closely as possible. In a randomized clinical trial, on average, treated and control groups are balanced with respect to pre-treatment characteristics. The analysis of the entire randomized sample will give the unbiased estimate of the causal effect in the entire trial eligible population. Any "selection" of individuals after randomization could lead to covariate imbalance, change in the population for whom the result may apply, and biased treatment effect estimates. PS methods attempt to emulate the process of randomization by using only pre-treatment covariates (blinded to outcomes and other follow-up observations) to control for potential confounding. We propose a PS model building

process that will estimate a PS for each patient in the entire eligible cohort to be used in analyses of all study objectives.

Information bias. Observational studies relying on retrospective data collection are at risk of information bias, as the accurate assessment of exposures, outcomes and key covariates may be challenged by issues such as the timing of clinical assessments, criteria for treatment response, and documentation in the EMR that vary between and within sites. Objective measures of outcomes and other variables at predefined time points will be used where possible. All data for eligible patients will be extracted and data from multiple sources will be deterministically linked to create a more complete capture of the patient journey. For the external control arm, information on confounders will be limited to data as it is documented in the patient's record.

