6.2 Demographics and Baseline Characteristics

The OM1 team will identify an eligible pool of patients for an external control arm in the OM1 PremiOM RA dataset.

The baseline study data from the PrismRA arm will be provided by the Scipher Medicine team in a format ready for analysis (fully quality controlled), with a corresponding dataset specification document to help the OM1 team understand the data.

From the pool of the study-eligible RA patients in the OM1 PremiOM RA dataset, the external control patients based on propensity score matching will be selected.

Baseline covariates including the following listed in **Table 4** will be considered (defined in a 6-month window prior to the index date unless otherwise specified elsewhere).

Table 4. Baseline covariates

Domain	Variables
Patient Characteristics	
 • Age (calculated from birth year) • Sex • Race/Ethnicity • Geography • Body mass index

Lifestyle	
 • Smoking (current, former, or never smoker)
Comorbidities (based on at least two diagnostic codes at least 30 days apart in the external control arm; based on an additional questionnaire in the PrismRA arm.)	
 • Lung disease • Myocardial infarction • Other cardiovascular • Stroke • Hypertension • Fractures spine, hip, or leg • Depression • Diabetes mellitus • Ulcer or stomach problem • Fibromyalgia 
The Rheumatic Disease Comorbidity Index (RDCI) will be derived.

RA Related	
 • Duration of RA (Defined as the number of days between the date of the first RA diagnosis code and the index date for the external control arm) • Seropositivity (rheumatoid factor or anti-citrullinated peptide antibody) • CDAI at baseline • Previous use of TNFi (yes, no)
Concurrent RA Medications	
 • Methotrexate • Folic acid • Non-methotrexate major csDMARDs (Sulfasalazine, Leflunomide, Hydroxychloroquine) • Glucocorticoids (with prednisone equivalent dose)

The choice of TNFi vs. non-TNFi b/tsDMARDs as the study treatment will be excluded from the list of potential propensity score variables, as this variable is temporally subsequent to the study's exposure variable (use or non-use of PrismRA in the PrismRA arm and external control arm, respectively) and is considered a mediator of the potential benefit of PrismRA.

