6.3.1 Main Analysis

Main analyses will proceed according to the following order of procedures:

- 1) Perform single imputation for all missing pre-treatment covariates.
- 2) Estimate the probability of treatment with PrismRA for matching. Only pre-treatment covariates will be included as predictors of treatment (e.g., blinded to outcomes).
- 3) Perform stratified PS matching and describe patient characteristics of this single matched cohort. Matched external control arm should be weighted following the principle in Section 6.3 before describing patient characteristics.
- 4) Impute missing outcome data using MI as described in Section 5.4.
- 5) Within each imputed dataset, fit treatment effect outcome model with arm assignment as the independent variable with covariates adjustment.
- 6) Pool treatment effect estimates using Rubin's rule.

Steps 1-4 will be performed once at the start of analyses for each analysis population. Steps 5 and 6 will be repeated for each study endpoint and for the Treatment Policy Strategy and Composite Strategy.

Outcome regression models may also include direct adjustment for important patient covariates (e.g. age, sex, race/ethnicity, RDCI, baseline scores). In general, these methods improve confounding control in cases of imperfect matching and stratification. [30] The proportion of patients within each study arm with moderate or high disease activity at baseline who achieve an MID in CDAI of ≥ 6 (baseline moderate) or ≥ 12 (baseline high) at 24 weeks after study treatment initiation will be reported. Odds ratio and 95% CI will be estimated using weighted logistic regression.

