Glucocorticoids	Yes	xxx (xx%)	xxx (xx%)	x.xx
	No	xxx (xx%)	xxx (xx%)	

Footnotes

¹ Using all available data before the index date comorbidities are based on the presence of at least two diagnostic codes at least 30 days apart in the external control arm; based on an additional questionnaire in the PrismRA arm.

² Rheumatoid factor or anti-citrullinated peptide antibody.

The following tables will be created using the same layout as Table 1.1.

Table 1.2 Baseline characteristics of modified ITT cohort by study arms after PSM

Table 1.1.1 Baseline characteristics of modified ITT cohort by study arms for TNFi-naïve group before PSM

Table 1.1.2 Baseline characteristics of modified ITT cohort by study arms for TNFi-exposed group before PSM

[figure not shown]
Table 1.2.1 Baseline characteristics of modified ITT cohort by study arms for TNFi-naïve group after PSM

Table 1.2.2 Baseline characteristics of modified ITT cohort by study arms for TNFi-exposed group after PSM

Table 1.3 Baseline characteristics of PrismRA-adherent cohort by study arms before PSM

Table 1.4 Baseline characteristics of PrismRA-adherent cohort by study arms after PSM

Figure 2.1 PS overlap for modified ITT cohort before and after PSM

Programmer note: The figure above is an example figure showing propensity score distributions by study arm before (left panel) and after (right panel) matching.

[figure not shown]
The following figures will be created using the same layout as Figure 2.1.

Figure 2.1.1 PS overlap for modified ITT cohort for TNFi-naïve group before and after PSM

Figure 2.1.2 PS overlap for modified ITT cohort for TNFi-exposed group before and after PSM

Figure 2.2 PS overlap for PrismRA-adherent cohort before and after PSM

Figure 3.1 Baseline covariate balance plots for modified ITT cohort before and after PSM

Programmer note: The figure above is an example figure showing absolute standardized differences before (diamond) and after (circle) matching.

The following figures will be created using the same layout as Figure 3.1.

Figure 3.1.1 Baseline covariate balance plots for modified ITT cohort for TNFi-naïve group before and after PSM

Figure 3.1.2 Baseline covariate balance plots for modified ITT cohort for TNFi-exposed group before and after PSM

Figure 3.2 Baseline covariate balance plots for PrismRA-adherent cohort before and after PSM

Table 2.1 Primary and secondary composite strategy study endpoints for modified ITT cohort by study arm

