Study endpoint	PrismRA	Control	Odds ratio (95% CI)
CDAI MID at 24 weeks	n/N (%)	n/N (%)	x.xx (x.xx-x.xx)
CDAI MID at 12 weeks	n/N (%)	n/N (%)	x.xx (x.xx-x.xx)
CDAI LDA or Remission at 24 weeks	n/N (%)	n/N (%)	x.xx (x.xx-x.xx)
CDAI LDA or Remission at 12 weeks	n/N (%)	n/N (%)	x.xx (x.xx-x.xx)
PtGA MCID at 24 weeks	n/N (%)	n/N (%)	x.xx (x.xx-x.xx)
PtGA MCID at 12 weeks	n/N (%)	n/N (%)	x.xx (x.xx-x.xx)
RAPID3 MCID at 24 weeks	n/N (%)	n/N (%)	x.xx (x.xx-x.xx)
RAPID3 MCID at 12 weeks	n/N (%)	n/N (%)	x.xx (x.xx-x.xx)
Pain VAS MCID at 24 weeks	n/N (%)	n/N (%)	x.xx (x.xx-x.xx)
Pain VAS MCID at 12 weeks	n/N (%)	n/N (%)	x.xx (x.xx-x.xx)
ACR50 at 24 weeks	n/N (%)	n/N (%)	x.xx (x.xx-x.xx)
ACR50 at 12 weeks	n/N (%)	n/N (%)	x.xx (x.xx-x.xx)

Programmer note: N= number of patients with moderate or high disease activity; n= number of patients achieving endpoint criteria

The following Tables will be created using the same layout as Table 2.1.

Table 2.1.1 Primary and secondary composite strategy study endpoints for modified ITT cohort by study arm for TNFi-naïve group

Table 2.1.2 Primary and secondary composite strategy study endpoints for modified ITT cohort by study arm for TNFi-exposed group

Table 2.2 Primary and secondary treatment policy strategy study endpoints for modified ITT cohort by study arm

Table 2.2.1 Primary and secondary treatment policy strategy study endpoints for modified ITT cohort by study arm for TNFi-naïve group

Table 2.2.2 Primary and secondary treatment policy strategy study endpoints for modified ITT cohort by study arm for TNFi-exposed group

Table 2.3 Primary and secondary composite strategy study endpoints for PrismRA-adherent cohort by study arm

Table 2.4 Primary and secondary treatment policy strategy study endpoints for PrismRA-adherent cohort by study arm

Table 3.1 CDAI change from baseline at 12 and 24 weeks for modified ITT cohort by study arm

Characteristic		PrismRA N = xxx	Control N = xxx	Average difference (95% CI)
CDAI at baseline	n	xxx	xxx	
	Mean (s.d.)	xxx (xx.x)	xxx (xx.x)	xxx (xxx-xxx)
	Median (Q1-Q3)	xxx (xxx-xxx)	xxx (xxx-xxx)	
CDAI at 12 weeks	n	xxx	xxx	
	Mean (s.d.)	xxx (xx.x)	xxx (xx.x)	xxx (xxx-xxx)
	Median (Q1-Q3)	xxx (xxx-xxx)	xxx (xxx-xxx)	
Change in CDAI at 12 weeks	n	xxx	xxx	
	Mean (s.d.)	xxx (xx.x)	xxx (xx.x)	xxx (xxx-xxx)
	Median (Q1-Q3)	xxx (xxx-xxx)	xxx (xxx-xxx)	
CDAI at 24 weeks	n	xxx	xxx	
	Mean (s.d.)	xxx (xx.x)	xxx (xx.x)	xxx (xxx-xxx)
	Median (Q1-Q3)	xxx (xxx-xxx)	xxx (xxx-xxx)	

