Change in CDAI at 24 weeks	n	xxx	xxx	
	Mean (s.d.)	xxx (xx.x)	xxx (xx.x)	xxx (xxx-xxx)
	Median (Q1-Q3)	xxx (xxx-xxx)	xxx (xxx-xxx)	

The following Tables will be created using the same layout as Table 3.1.

Table 3.1.1 CDAI change from baseline at 12 and 24 weeks for modified ITT cohort by study arm for TNFi-naïve group

Table 3.1.2 CDAI change from baseline at 12 and 24 weeks for modified ITT cohort by study arm for TNFi- exposed group

Table 3.2 CDAI change from baseline at 12 and 24 weeks for PrismRA-adherent cohort by study arm

The following Table will be created using the same layout as Table 2.1.

Table 4 Sensitivity analyses of primary and secondary composite strategy study endpoints for modified ITT cohort by study arm

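### The PrismRA-adherent tables drop signature-positive TNFi starters from one arm only, so their between-arm estimates mix following the result with a change in who is compared

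*SAP*

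**What the plan says.** SAP 5.2 defines two populations from the PrismRA arm: the modified ITT population and a sub-population adherent to the test. For the second, "This sub-population will exclude patients who initiated TNFis despite having a PrismRA result indicating a molecular signature of non-response to TNFi therapies". No counterpart rule is given for the external control arm, and none is possible. The external-control table in Protocol 8.6 marks PrismRA as not applicable, and Protocol 9.2 says of the controls: "Data arise from routine clinical practice and do not involve the use of the PrismRA test".

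The cohort is still compared between arms:
- "Table 2.3 Primary and secondary composite strategy study endpoints for PrismRA-adherent cohort by study arm", with Table 2.4 as the treatment-policy version; both use a layout with odds ratios and 95% CIs.
- "Table 3.2 CDAI change from baseline at 12 and 24 weeks for PrismRA-adherent cohort by study arm", in a layout with average differences and 95% CIs.

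Matching is repeated for this cohort, since SAP 6.3.1 says "Steps 1-4 will be performed once at the start of analyses for each analysis population". The covariates are those of SAP Table 4, which lists neither the signature nor the PrismRA score. SAP 6.2 keeps the choice between TNFi and non-TNFi out of the propensity model because it follows the exposure and "is considered a mediator of the potential benefit of PrismRA".

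**The concern.** The cohort is selected on a post-exposure choice that the SAP itself treats as a mediator, jointly with a test result that only one arm has. After the exclusion the PrismRA side holds fewer signature-positive patients, while the control side keeps its full share. SAP 5.5 gives the general warning: selection "of individuals after randomization could lead to covariate imbalance, change in the population for whom the result may apply, and biased treatment effect estimates".

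In a clinical-utility study, an odds ratio for an adherent cohort invites the reading that this is the benefit when the result is followed. No label or caution in the SAP guards against that reading. The planned balance check ("Table 1.4 Baseline characteristics of PrismRA-adherent cohort by study arms after PSM") cannot reveal the shift in signature mix, because controls are untested.

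**Working it through.** The plan gives no figure for this point, so there is none to reproduce. What follows shows how the distortion behaves and is not an estimate of it.

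**Inputs**
- From the documents: 600 PrismRA patients (SAP 5.1); odds ratios of 3.4 to 8.8 for TNFi response by signature in targeted-therapy-naïve patients (Protocol 5.1). These odds ratios are not tied to the CDAI MID endpoint.
- Assumed: signature-positive share f = 40-60%; share of these given a TNFi anyway g = 10-50%; TNFi use among signature-negatives t = 70%; mean response on TNFi 30%; non-TNFi response r = 30%, 40% or 50%, the same for both signature groups.
- Also assumed: re-matching leaves the control response unchanged. No allowance is made for covariate adjustment in the outcome model.

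**Formula.** Let A be the response of those kept, s the response the excluded would have had if they had followed the result, and C the control response.
- Adherent estimate = A - C.
- Full-adherence effect = (1 - fg)A + fg·s - C.
- Excess = fg(A - s).

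The excluded share fg runs from 0.4 × 0.1 = 4% to 0.6 × 0.5 = 30%, or 24 to 180 of 600. Each 10-point gap between A and s therefore moves the estimate by 0.4 to 3.0 points, in the direction of the gap.

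**One case worked through** (f = 50%, g = 30%, OR 3.4 on TNFi only)
- TNFi response p (signature-negative) and q (signature-positive) solve 0.5q + 0.5p = 0.30 with odds(p) = 3.4 × odds(q), giving q = 17.7% and p = 42.3%.
- The signature-positive share falls to (0.50 - 0.15)/0.85 = 41% among those kept, against 50% in controls.
- If r = 30%: signature-negatives respond at 0.7 × 42.3 + 0.3 × 30 = 38.6%. A = (0.35 × 30 + 0.50 × 38.6)/0.85 = 35.1%. Excess = 0.15 × (35.1 - 30) = +0.8 points.
- If r = 50%: signature-negatives respond at 44.6%. A = (0.35 × 50 + 0.50 × 44.6)/0.85 = 46.8%. Excess = 0.15 × (46.8 - 50) = -0.5 points.

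**Full range** (f 40-60%, g 10-50%, OR 3.4-8.8)

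| Non-TNFi response | Excess over full adherence, points |
|---|---|
| 30% | +0.2 to +3.1 |
| 40% | -0.1 to +1.9 |
| 50% | -1.1 to +0.7 |

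**The target matters.** Suppose the result is ignored: f = g = t = 50%, r = 30%. Modified ITT response is then 30.0% in both arms, a difference of 0. Results for OR 3.4 / 8.8:
- Response of those kept: 34.1% / 36.6%, so the adherent table shows +4.1 / +6.6 points.
- Full-adherence response: 33.1% / 35.0%, a true effect of +3.1 / +5.0. The error is +1.0 / +1.7.
- If the target is instead the ATT (the estimand in SAP 6.3) among those kept, their own standard-care response is the comparator. That is 32.0% / 33.3%, against 30.0% in the controls used. The error is +2.0 / +3.3.

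**The case against.** Several objections stand.
- The SAP says only that the sub-population will be analysed as well. A reader might infer that Tables 2.3, 2.4 and 3.2 are offered as the isolated effect of following the result, but no sentence says so. This is a per-protocol-type supplement beside an unaffected modified ITT analysis.
- The number excluded is recoverable: PrismRA-arm N in Table 1.1 minus N in Table 1.3, both before matching. Comparing those tables also gives much of the baseline profile. Only the response the excluded would have had is out of reach.
- The absent signature row in Table 1.4 is not a separate fault, since untested controls could not fill it.
- SAP 5.5 speaks of selection after randomisation, and Protocol 8.8.1 says there is none here. It applies by analogy, through the SAP's stated aim of emulating a randomised trial.
- Deleting the between-arm tables would be a preference; clear labelling meets most of the harm.

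A reader might also infer that the exclusion must favour PrismRA. The documents do not support that. Protocol 5.1 reports poorer response with the signature on TNFi only. The uniformly positive range above depends on setting non-TNFi response at 30%, and at 40% or 50% the range crosses zero. Larger figures (+1.2 to +7.4 points at 20-50% override) require the signature to lower response on every drug, which the documents do not show.

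None of this removes the asymmetry. Ordinary per-protocol rules can be applied to both arms; this one cannot.

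**Conclusion.** The point holds as a limit on interpretation. The exclusion is one-sided by construction, it cannot be mirrored in untested controls, and re-matching on Table 4 cannot be relied on to undo it. The adherent between-arm estimates therefore combine an effect of following the result with a change in patient mix.

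The documents fix neither size nor direction. Under the assumptions shown, the distortion ranges from about -1 to +3 points against full adherence, beside a planned difference of 10 points. It is zero if the excluded patients, had they followed the result, would have responded like those kept. Confidence is high for the one-sided selection and low for its size and sign. Severity is minor to moderate and confined to a supportive analysis.

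**What to change.** 1. State that conclusions rest on the modified ITT comparison.
2. For the adherent analysis, keep the modified ITT matched set with all its controls. Within each imputed dataset, weight signature-positive patients who followed the result by the inverse probability of following it. Model that probability on baseline covariates, the PrismRA score and, where informative, questionnaire answers given before the treatment decision. Use robust standard errors.
3. Label the result supportive, and state the untestable assumption that measured covariates explain who followed the result.
4. Within the PrismRA arm, report the number, baseline profile and PrismRA score of those excluded.
5. If the unweighted Tables 2.3, 2.4 and 3.2 are kept, label them descriptive and not an estimate of the effect of following the result.

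The cost is one extra model, to be combined with the matching weights and multiple imputation, and wider confidence intervals. No new data are needed.

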5.3 Data Summarization and Analysis

Summary statistics for continuous variables to be reported will include mean, median, standard deviation (SD), 25th and 75th percentile. Categorical variables will be reported using counts and proportions. Hypothesis testing will be two-sided with an alpha level of 5%. For all outcome measures, point estimates as well as two-sided 95% confidence intervals (CIs) will be provided. P-values will be reported where appropriate to four decimal points unless all p-values in a table are greater than 0.01 in which case p-values will be reported to three decimal points in that table as the fourth decimal point is not needed. Details of the specific analytic methods are described below (Section 6).

